9.1 Adverse Events

It is the responsibility of the Investigator to document all AEs that occur during the study.

Adverse event is defined as any untoward medical occurrence associated with the use of a drug in humans, whether or not considered drug related.

Life-threatening adverse event or life-threatening suspected adverse reaction: An adverse event or suspected adverse reaction is considered "life-threatening" if, in the view of either the Investigator or Sponsor, its occurrence places the patient or subject at immediate risk of death. It does not include an adverse event or suspected adverse reaction that, had it occurred in a more severe form, might have caused death.

An AE includes any noxious, pathological, or unintended change in anatomical, physiological, or metabolic functions as indicated by physical signs or symptoms occurring in any phase of the clinical study whether or not considered related to the study medication. This definition includes an exacerbation of preexisting medical conditions or events, historical condition not present prior to study treatment, which reappear following study treatment, intercurrent illnesses, hypersensitivity reactions, drug interaction, or the significant worsening of the disease under investigation that is not recorded elsewhere in the CRF. Anticipated day-to-day fluctuations of pre-existing conditions that do not represent a clinically significant exacerbation or worsening need not be considered AEs.

Any laboratory abnormality fulfilling the criteria for a SAE (Section 9.2) should be reported as such, in addition to being recorded as an AE. Any treatment-emergent abnormal laboratory result which is clinically significant, ie, meeting 1 or more of the following conditions, should be recorded as a single diagnosis AE:

- Is considered to be an SAE,
- Results in discontinuation from study treatment, or
- Results in a requirement for a change in concomitant therapy (ie, addition of concomitant therapy)

In the event of medically significant unexplained abnormal laboratory test values, the tests should be repeated and followed up until they have returned to the normal range and/or an adequate explanation of the abnormality is determined.

TEAEs are defined as any AEs reported after the first dose of study drug on Day 1. Adverse events reported after consent of a patient, but before administration of study medication, will be reported in the Medical History.

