9.2 Serious Adverse Events (SAEs)

An SAE is defined as any event that results in any of the following outcomes:

1. Death
2. A life-threatening adverse event;
3. Inpatient hospitalization or prolonging of an existing hospitalization (see [Section 9.2.1](#) for information on hospitalization as an SAE);

4. A persistent or significant incapacity or substantial disruption of the ability to conduct normal life functions; or
5. A congenital anomaly/birth defect.

Important medical events that may not result in death, be life-threatening, or require hospitalization may be considered serious when, based upon appropriate medical judgment, they may jeopardize the subject and may require medical or surgical intervention to prevent one of the outcomes listed above.

Any SAE must be reported by telephone or facsimile within 24 hours of discovery of the event. Investigators should not wait to receive additional information to fully document the event before notifying the Sponsor of an SAE at:

Sites in North America must report to:

Safety Data [contact]

Safety [contact]

Email address (in case of fax failure): [contact]

Sites outside North America must report to the country specific toll-free fax numbers identified below:

Australia: [REDACTED]
Belgium: [REDACTED]
Brazil: [REDACTED]
France: [REDACTED]
Germany: [REDACTED]
Israel: [REDACTED]
Italy: [REDACTED]
Netherlands: [REDACTED]
Spain: [REDACTED]
Sweden: [REDACTED]
United Kingdom: [REDACTED]

Email Address (in case of fax failure): [REDACTED]

The telephone report should be followed by full written summary detailing relevant aspects of the SAE in question using the provided SAE report form. Where applicable, information from relevant hospital case records and autopsy reports should be obtained. The SAE should also be recorded on the AE page of the patient's CRF.

An SAE that occurs after completion of the study but, in the opinion of the Investigator, is related to the study medication, should be reported as described for an SAE. If an AE does not meet the regulatory definition of "serious" but is considered by the Investigator to be

related to the study medication and of such clinical concern as to influence the overall assessment of safety, it must be reported as defined for an SAE.

All patients (including discontinued patients) with a SAE must be followed until the event resolves or reaches a new Baseline, but for a minimum of 30 days after the last dose of study drug.

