10.1 Determination of Sample Size

No formal sample size calculation was made. The number of patients expected to participate in this study was calculated from estimated enrollment rates from other carcinoid cancer trials employed in the LX1606 clinical program.

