10.3.2 Safety Endpoints

Safety endpoints are as follows:

- Incidence of TEAEs, suspected adverse reaction, AEs leading to discontinuation from the study, SAEs, and deaths
- Actual and change from Baseline in clinical laboratory results
- Actual and change from Baseline in vital signs results
- Actual and change from Baseline in physical examinations
- Actual and change from Baseline in ECG findings

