10.4.2.1 Adverse Events

All AEs will be coded and listed by body system and preferred term based on the Medical Dictionary for Regulatory Activities (MedDRA). Summaries using descriptive statistics will be provided for treatment-emergent AEs, drug-related AEs and AEs by intensity. Treatment-

emergent AEs are those events not present at Baseline, but occurring after the start of study drug, or if existing at Baseline, increasing in intensity after initiation study drug. Summaries made by intensity will select the event with the highest intensity when multiple occurrences of the same event are reported for the same patient. In a similar manner, summaries prepared by drug relationship will select the event with the greatest degree of relationship when a study reports multiple occurrences of the same event. On-study deaths will be reported for deaths occurring during the active phase of the treatment period and 30 days after stopping study drug. Also, deaths occurring outside the 30-day window, but secondary to an AE reported within the 30-day post treatment period, will be reported as well.

Listings will be provided for deaths, SAEs, and discontinuations due to AEs. Additional summaries or listings of AEs may also be provided.

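### The late-death rule leaves deaths from AEs reported during treatment out of the on-study death count

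*Protocol*

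**What the plan says.** Section 10.4.2.1 gives two routes by which a death is reported as on-study.

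- By date of death, whatever the cause: "On-study deaths will be reported for deaths occurring during the active phase of the treatment period and 30 days after stopping study drug".
- By cause, for later deaths: "deaths occurring outside the 30-day window, but secondary to an AE reported within the 30-day post treatment period, will be reported as well".

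No third route is given. The same two sentences stand in the other versions of the protocol reproduced in the file.

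Four other statements bear on the point. Section 10.3.2 lists as a safety endpoint: "Incidence of TEAEs, suspected adverse reaction, AEs leading to discontinuation from the study, SAEs, and deaths". It sets no time window for deaths. Section 10.4.2.1 also promises: "Listings will be provided for deaths, SAEs, and discontinuations due to AEs". Section 9.2 requires that "All patients (including discontinued patients) with a SAE must be followed until the event resolves or reaches a new Baseline", with a minimum of 30 days after the last dose. Section 9.1 opens the treatment-emergent window at the first dose: "TEAEs are defined as any AEs reported after the first dose of study drug on Day 1".

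**The concern.** The second route appears meant to catch deaths that fall after the 30-day cut-off but result from an event linked to exposure. It ties the causal event to the post-treatment month only. An event reported during treatment is at least as relevant to the drug as one first reported after stopping, yet only the latter brings a late death into the count.

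The omission is selective. The late deaths that fall out are those from events already on record during exposure, which can include events that led to stopping. In a study whose primary objective is long-term safety and tolerability, the on-study death count should not be lower because an event was recorded earlier.

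This is not a detail left to the SAP. The protocol states a rule, and an SAP that follows it takes over the gap.

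**Working it through.** The protocol states no death count, sample-size calculation or error rate on this point, so there is no figure to reproduce. The check applies the two sentences of Section 10.4.2.1 to each combination of date of death and date on which the causal AE was reported.

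| Death, relative to stopping drug | Causal AE reported | Route 1 (date of death) | Route 2 (cause) | On-study death? |
|---|---|---|---|---|
| On treatment or within 30 days | Any time | Met | Not needed | Yes |
| More than 30 days | In the 30 days after stopping | Not met | Met | Yes |
| More than 30 days | During treatment | Not met | Not met | **No** |
| More than 30 days | More than 30 days after stopping | Not met | Not met | No |

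The first, second and fourth rows are coherent. The third is the gap.

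A hypothetical pair shows it with only the report date changed. Both patients stop drug on Day 210, so the 30-day window ends on Day 210 + 30 = Day 240. Both die on Day 241, which is 241 − 210 = 31 days after stopping, so route 1 fails for both.

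- Patient 1: the fatal AE is reported on Day 200, on drug. The patient continues drug for 210 − 200 = 10 days and then stops. The report precedes the post-treatment period, so route 2 fails and the death is not counted.
- Patient 2: the fatal AE is first reported on Day 211, which is 211 − 210 = 1 day after stopping. Route 2 is met and the death is counted.

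Three comparisons within the protocol bear on whether this could be intended.

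1. The first sentence of the rule separates the active treatment phase from the 30 days after stopping. The post-treatment period in the next sentence therefore most naturally means the latter alone.
2. The treatment-emergent window in Section 9.1 starts at the first dose. The causal-AE window in the late-death rule starts only when drug is stopped.
3. Section 9.2 follows SAEs, including those in discontinued patients, to resolution or a new Baseline. The protocol therefore expects to learn the late outcome of SAEs reported on drug, but its on-study rule has no place for the late fatal ones.

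The number of deaths affected cannot be derived. It would need the rate of fatal AEs, the time from report to stopping and the time from stopping to death, and the protocol gives none of these.

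**The case against.** The strongest reply is that little is lost. Section 10.4.2 says all safety data will be listed, and the death listing in Section 10.4.2.1 has no window. The deaths endpoint in Section 10.3.2 carries no on-study restriction. A fatal AE reported on drug is also a treatment-emergent SAE and enters those summaries. The study is open-label and uncontrolled, its safety analysis is descriptive, and no comparison or boundary depends on the on-study death count. The intended meaning can also be guessed. All of this stands, and it keeps the point minor. It does not repair the count: a listing shows the individual death, while the rule still decides which deaths are labelled on-study, and it is the only rule for counting deaths in the statistical section.

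A second reply is that the rule turns on when the AE was reported, not when it began. This also stands, and it limits the point. A reader might infer that every late death from an AE that began on drug is left out. The text does not support that: an event that began on drug but was first reported in the 30 days after stopping is covered. A reader might likewise cite a patient who stops drug on the day the event occurs. Section 9.2 allows 24 hours from discovery to report an SAE, so that report may fall after stopping and the death may be counted. The clear case is an AE reported on drug, with drug continued for a time before it is stopped.

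**Conclusion.** The rule is wrong as written; the point is minor. On the literal text, a death more than 30 days after stopping drug and secondary to an AE reported during treatment is not an on-study death, whereas the same death from an AE first reported in the 30 days after stopping is.

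This rests on reading the post-treatment period as the 30 days after stopping, as the preceding sentence of the rule suggests. If the sponsor meant a window from first dose to 30 days after the last dose, the sentence needs correcting to say so.

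Two stronger conclusions are not supported. One is that these deaths disappear from reporting: they may still be seen in the death and SAE listings, and only the on-study count is affected. The other is any percentage of fatal AEs left uncounted. An assumed survival curve would give the share of deaths beyond 30 days, not the share that also fails the second route. No size can be stated beyond the direction: the count can only be too low, probably by a small number.

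**What to change.** Replace the second sentence of the rule in Section 10.4.2.1, and any matching SAP text, with wording such as:

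*Deaths occurring more than 30 days after the last dose that are secondary to a treatment-emergent AE (new, or worsened from Baseline) that occurred or was reported from the first dose in this study through 30 days after the last dose will also be reported as on-study deaths.*

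Two features of the wording matter. Accepting either occurrence or report keeps every late death that the present rule captures through an event first reported after stopping. Naming events that worsened from Baseline matters because patients roll over from earlier studies and Section 10.4.2.1 itself treats such worsening as treatment-emergent. A window based on onset alone would exclude a carried-over event that worsened here and proved fatal.

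The cost is one sentence. No new data, visits or procedures are needed, and no sample size or error rate changes. The reported on-study death count may rise slightly.

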10.4.2.2 Clinical Laboratory Parameters

Laboratory results will be reported in conventional units in all tables, figures, and listings. Laboratory results falling out of the normal range will be marked as high or low in the listings. Actual and changes from Baseline (Day 1) in clinical laboratory results will be summarized by using descriptive statistics. Summaries of shifts from Baseline to abnormal clinical laboratory results will also be provided. Actual and change from Baseline in chromogranin A levels will be summarized descriptively as well.

10.4.2.3 Vital Sign Measurements

Actual and changes from Baseline (Day 1) in vital signs results will be summarized by using descriptive statistics.

10.4.2.4 Electrocardiograms

Clinically significant changes in ECGs compared to Baseline, as determined by the Investigator, will be summarized by using descriptive statistics. Actual and change from Baseline (Day 1 pre-dose values) to each time point in corrected QT interval (QTcF) will be summarized as well.

10.4.3 Pharmacodynamic Analyses

Analysis and summarization of the plasma 5-HIAA data are described in [Section 10.4.1](#).

10.4.4 Baseline Characteristics and Other Summaries

Treatment group differences will be summarized descriptively for demographic data, prior and concomitant medications, treatment compliance, and final disposition. Data collected from assessments of tumor status, when available, will be listed.

Protocol deviations will be provided as listings.

10.4.5 Interim Analysis

An independent DSMB will be charged with reviewing interim safety data on a quarterly basis and reporting its recommendations to Lexicon Pharmaceuticals, Inc. Appropriate procedures will be detailed in a DSMB Charter that defines accessibility and disclosure of the interim study results.

The study may be analyzed and reported in multiple phases. The first report will summarize data obtained from all patients providing information up to a specified data cut-off point. The following reports will update the initial report by including data from the remaining portion of the study. The first reporting of the data may be taken as an interim analysis in terms of the procedural efforts needed to summarize these data, but it will not serve as a means to modify the analysis/study conduct.

11. Study Management

The Investigator is responsible for completing and maintaining adequate and accurate CRFs and source documentation. Source documentation constitutes original records, which may include: progress notes, medication administration records, laboratory reports, ECG tracings, and discharge summaries.

All data on the CRF must be recorded in accordance with the CRF guidelines. If a correction is necessary, it should be made by the Investigator or a designated qualified individual as specified within the guideline. All CRFs should be completed in their entirety and stored in a secure location. The Investigator must sign the Investigator's statement in each patient's CRF indicating that the data reported are accurate.

At the study site, clinical research associates will verify 100% of CRFs in their entirety against source documentation. Computer programmed edit checks will be run against the database to check for discrepancies and reasonableness of the data, and the safety database will be reconciled with the clinical database. All issues resulting from the computer generated checks and the safety database reconciliation will be resolved according to standard data management practices in conjunction with the Sponsor, clinical study personnel, and the study Investigators.

11.1 Monitoring

The Sponsor is responsible for ensuring the proper conduct of the study with regard to ethics, protocol adherence, site procedures, integrity of the data, and applicable laws and/or regulations. At regular intervals during the study and following completion of the study, the

Sponsor's study monitors will contact the study site via visits to the site, telephone calls, and/or letters in order to review study progress, CRF completion, and address any concerns or questions regarding the study conduct. During monitoring visits, the following aspects of study conduct will be carefully reviewed: informed consent of patients, patient recruitment, patient compliance with the study procedures, source data verification, drug accountability, use of concomitant therapy by patients, AE and SAE documentation and reporting, and quality of data. Records pertaining to these aspects are expected to be kept current.

The Investigator must make study data accessible to the clinical monitor, to other authorized representatives of the Sponsor, and to regulatory inspectors

11.2 Audits and Inspections

The Sponsor, regulatory authority, or IRB/ERC may visit the study site at any time during the study or after completion of the study to perform audits or inspections. The purpose of a Sponsor audit or regulatory inspection is to systematically and independently examine all study-related activities and documents to determine whether these activities were conducted according to the protocol, GCP, ICH guidelines, and any other applicable regulatory requirements. Investigators should contact the Sponsor immediately if contacted by a regulatory agency about an inspection at their site.

11.3 Amendments

Any amendments to the protocol will be written and approved by the Sponsor. All amendments must be submitted to the IRB/ERC for approval prior to implementing the changes. In some instances, an amendment may require changes to the informed consent form, which also must be submitted for IRB/ERC approval prior to administration to patients. If any changes to the CRF are required, the Sponsor will issue supplemental or revised CRF pages.

11.4 Record Keeping

11.4.1 Drug Accountability

The Investigator must maintain accurate records of receipt of study drug, dispensing information (date, lot, and dose for each patient), and the prompt return or destruction of unused supplies. If the Investigator cannot account for all clinical supplies at the termination of the study, a written explanation must be provided.

11.4.2 Health Insurance Portability Accountability Act of 1996 and Subsequent Updates

The Investigator agrees to comply with all applicable federal, state, and local laws and regulations relating to the privacy of patient health information, including, but not limited to, the Standards for Individually Identifiable Health Information, 45 Code of Federal Regulations (CFR) Parts 160 and 164 (the Health Insurance Portability Accountability Act of 1996 [HIPAA] Privacy Regulation and any applicable updates). The Investigator shall ensure that study patients authorize the use and disclosure of protected health information in accordance with HIPAA Privacy Regulation and in a form satisfactory to the Sponsor.

11.4.3 Financial Disclosure

The Investigator shall provide to the Sponsor sufficient accurate financial information to allow the Sponsor to submit complete and accurate financial certification or disclosure statements to the FDA and/or other applicable regulatory agencies. The Investigator shall promptly update this information if any relevant changes occur in the course of the study or for 1 year following completion of the study.

11.4.4 Access to Original Records

It is an expectation of regulatory authorities that monitors, auditors, and representatives of national and international government regulatory agency bodies have access to original source documentation (see examples in [Section 11](#)) to ensure data integrity. “Original” in this context is defined as the first documentation of an observation and does not differentiate between hard copy and electronic records.

11.4.5 Retention of Study Documents

According to 21 CFR Part 312.62 and ICH E6, study-related records must be retained for at least 2 years after the last approval of a marketing application in an ICH region and until there are no pending or contemplated marketing applications in an ICH region, or at least 2 years have elapsed since the formal discontinuation of clinical development of the investigational product. These documents should be retained for a longer period, however, if required by applicable regulatory requirements or by an agreement with the Sponsor.

The Investigator must not destroy any study-related records without receiving approval from the Sponsor. The Investigator must notify the Sponsor in the event of accidental loss or destruction of any study records. If the Investigator leaves the institution where the study was conducted, the Sponsor must be contacted to arrange alternative record storage options.

12. Administrative Structure of the Study

Lexicon Pharmaceuticals, Inc.
[name]
[name]

Protocol No. LX1606.302

The study will be monitored by Sponsor personnel or Sponsor representative. The following functions for this study will be performed by organizations designated by the Sponsor: data management and statistical analysis, including PD analysis and reporting.

21 January 2015

CONFIDENTIAL

Page 44 of 59

CONFIDENTIAL
FINAL 24 February 2016

Page 236

INTERIM CLINICAL STUDY REPORT
LX1606.1-302-CS

13. Appendix A – Schedule of Events

Procedure	Extension Period								2-Week Follow-up ⁴
	Baseline Day 1 ¹	Week 12	Week 24	Week 36	Week 48	Week 60	Week 72	Week 84 / EOS	
Tolerance (days)	NA	± 5	± 5	± 5	± 5	± 5	± 5	± 5	± 5
Inclusion/Exclusion criteria	X								
Medical history	X								
Physical examination incl. weight	X	X ³	X ³	X ³	X	X ³	X ³	X	X ⁵
Urine pregnancy test ²	X	X	X	X	X	X	X	X	X
Serum pregnancy test ²									
Hematology, Blood chemistry	X	X	X	X	X	X	X	X	X ⁵
Urinalysis	X				X			X	X ⁵
Chromogranin A	X				X			X	
Vital signs	X	X	X	X	X	X	X	X	X
ECG	X				X			X	X ⁵
Subjective Global Assessment	X	X	X	X	X	X	X	X	X
EORTC QLQ-C30 & GI.NET21	X		X		X		X	X	
Sleep and Depression Assessment	X	X	X	X	X	X	X	X	X
Plasma 5-HIAA	X	X	X	X	X	X	X	X	X
Dispensation of LX1606	X	X	X	X	X	X	X		
Concomitant medications	X	X	X	X	X	X	X	X	X
Adverse events	X	X	X	X	X	X	X	X	X

¹Eligibility will be determined at last visit of the original protocol; Day 1 will replace the next scheduled visit in the original protocol schedule. Visits should coincide with LAR injections for those patients receiving SSA therapy. ²Females of child-bearing potential only. ³Brief physical examination only (symptom-oriented, including weight). ⁴Visit to be performed for subjects who withdraw early and will not return for a 2-week follow-up visit; in all other cases the EOS visit should be performed followed by the follow-up visit 2 weeks postdose. ⁵To be performed only if evaluation at Week 48/84/EOS is abnormal.

14. Appendix B – Amount of Blood to be Collected from Each Patient

Assessment		Sample volume (mL)	Number of samples*	Estimated total volume (mL)
Safety	Hematology	2	9	18
	Blood chemistry	6	9	54
Other	CgA	2	3	6
Pharmacodynamic	Plasma 5-HIAA	4	9	36
Total				114
*Maximum number of samples is indicated				

During the past week:

	Not at All	A Little	Quite a Bit	Very Much
17. Have you had diarrhea?	1	2	3	4
18. Were you tired?	1	2	3	4
19. Did pain interfere with your daily activities?	1	2	3	4
20. Have you had difficulty in concentrating on things, like reading a newspaper or watching television?	1	2	3	4
21. Did you feel tense?	1	2	3	4
22. Did you worry?	1	2	3	4
23. Did you feel irritable?	1	2	3	4
24. Did you feel depressed?	1	2	3	4
25. Have you had difficulty remembering things?	1	2	3	4
26. Has your physical condition or medical treatment interfered with your family life?	1	2	3	4
27. Has your physical condition or medical treatment interfered with your social activities?	1	2	3	4
28. Has your physical condition or medical treatment caused you financial difficulties?	1	2	3	4

For the following questions please circle the number between 1 and 7 that best applies to you

29. How would you rate your overall health during the past week?

1 2 3 4 5 6 7

Very poor

Excellent

30. How would you rate your overall quality of life during the past week?

1 2 3 4 5 6 7

Very poor

Excellent

© Copyright 1995 EORTC Quality of Life Group. All rights reserved. Version 3.0

16. Appendix D – EORTC QLQ - GI.NET21

ENGLISH

EORTC QLQ – GI.NET21

Patients sometimes report that they have the following symptoms or problems. Please indicate the extent to which you have experienced these symptoms or problems during the past week. Please answer by circling the number that best applies to you.

During the past week:		Not at all	A little	Quite a bit	Very much	
31.	Did you have hot flushes?	1	2	3	4	
32.	Have you noticed or been told by others that you looked flushed/red?	1	2	3	4	
33.	Did you have night sweats?	1	2	3	4	
34.	Did you have abdominal discomfort?	1	2	3	4	
35.	Did you have a bloated feeling in your abdomen?	1	2	3	4	
36.	Have you had a problem with passing wind/gas/flatulence?	1	2	3	4	
37.	Have you had acid indigestion or heartburn?	1	2	3	4	
38.	Have you had difficulties with eating?	1	2	3	4	
39.	Have you had side-effects from your treatment? (If you are not on treatment please circle N/A)	N/A	1	2	3	4
40.	Have you had a problem from repeated injections? (If not having injections please circle N/A)	N/A	1	2	3	4
41.	Were you worried about the tumour recurring in other areas of the body?	1	2	3	4	
42.	Were you concerned about disruption of home life?	1	2	3	4	
43.	Have you worried about your health in the future?	1	2	3	4	
44.	How distressing has your illness or treatment been to those close to you?	1	2	3	4	
45.	Has weight loss been a problem for you?	1	2	3	4	
46.	Has weight gain been a problem for you?	1	2	3	4	
47.	Did you worry about the results of your tests? (If you have not had tests please circle N/A)	N/A	1	2	3	4
48.	Have you had aches or pains in your muscles or bones?	1	2	3	4	
49.	Did you have any limitations in your ability to travel?	1	2	3	4	
During the past four weeks:						
50.	Have you had problems receiving adequate information about your disease and treatment?	1	2	3	4	
51.	Has the disease or treatment affected your sex life (for the worse)? (If not applicable please circle N/A)	N/A	1	2	3	4

© QLQ-GI.NET21 Copyright 2004 EORTC Quality of Life Group. All rights reserved. Date: 20th February 2006

17. Appendix E – Ethical Standards

Ethics and Regulatory Considerations

This study will be conducted according to GCP, 21 CFR Part 50, (Protection of Human Subjects), 21 CFR Part 56 (Institutional Review Boards), International Conference on Harmonisation Guidance for Industry, E6 Good Clinical Practice: Consolidated Guidance, the Nuremberg Code, and the Declaration of Helsinki.

General Instructions

The FDA regulates studies of drugs, biologics, and medical devices. Consequently, these studies are subject to GCP regulations and guidance issued by the FDA and are included in, but not limited to, the following parts of the CFR and guideline document:

- 21 CFR Part 11 – Electronic Records
- 21 CFR Part 50 – Protection of Human Subjects
- 21 CFR Part 54 – Financial Disclosure
- 21 CFR Part 56 – Institutional Review Boards
- 21 CFR Part 312 – Investigational New Drug Application
- Current FDA Guideline for the Monitoring of Clinical Investigations
- Current Guidance for Institutional Review Boards and Clinical Investigators
- ICH E6 – Guidance for Industry, E6 Good Clinical Practice: Consolidated Guidance

Studies conducted in the European Union are also regulated by Volume 10 of the publications “The rules governing medicinal products in the European Union”.

Copies of these materials are available from the Sponsor upon request. The purpose of these regulations and legal obligations is to define the standards and principles for the proper conduct of clinical trials that have been developed by the medical, scientific, and regulatory communities. They are not intended to impede or restrict clinical research.

The ethical standards defined within GCP are intended to ensure that:

- human subjects are provided with an adequate understanding of the possible risks of their participation in the study, and that they have a free choice to participate or not;
- the study is conducted with diligence and in conformance with the protocol in such a way as to insure the integrity of the findings;
- the potential benefits of the research justify the risks.

Lexicon Pharmaceuticals, Inc. is the Sponsor of the IND. The Sponsor is responsible for the following:

- selecting qualified Investigators,
- providing Investigators with the information they need to properly conduct an investigation,
- ensuring proper monitoring of the investigation,
- ensuring that the study is conducted according to the general investigational plan and protocols contained in the IND,
- maintaining the IND, and
- ensuring that regulatory authorities and all participating Investigators are properly informed of significant new information regarding adverse effects or risks associated with the drug being studied
- ensuring the study is conducted in accordance to FDA and ICH guidelines and all applicable regulations

18. Appendix F – Investigator Obligations

Per Title 21 of the US Government Code of Federal Regulations (21 CFR) Parts 50 and 56 and ICH E6, the study protocol and the final version of the subject informed consent form will be approved by the IRB/ERC before enrollment of any subjects. The opinion of the IRB/ERC will be dated and given in writing. A copy of the letter of approval from the IRB/ERC and a copy of the approved informed consent form will be received by the Sponsor prior to shipment of study medication supplies to the Investigator.

The Investigator will ensure that the IRB/ERC will be promptly informed of all changes in the research activity and of all unanticipated problems including risk to subjects. The Investigator will also ensure that no changes will be made to the protocol without IRB/ERC approval.

As a part of the IRB/ERC requirement for continuing review of approved research, the Investigator will be responsible for submitting periodic progress reports to the IRB/ERC at intervals appropriate to the degree of subject risk involved, but no less than once per year.

Written informed consent must be given freely and obtained from every subject prior to clinical trial participation. The rights, safety, and well-being of the trial subjects are the most important considerations and should prevail over interests of science and society.

As described in GCP guidelines, study personnel involved in conducting this trial will be qualified by education, training, and experience to perform their respective task(s). Study personnel will not include individuals against whom sanctions have been invoked after scientific misconduct or fraud (eg, loss of medical licensure, debarment). Quality assurance systems and procedures will be implemented to assure the quality of every aspect of the study.

Principal Investigators must provide Lexicon with a fully executed Form FDA 1572 (statement of Investigator) and all updates on a new fully executed Form FDA 1572.

Principal Investigators must provide Lexicon with his/her own curriculum vitae and current curriculum vitae for each sub-Investigator listed on Form FDA 1572.

Protection of Human Subjects (21 CFR Part 50 and ICH E6)

Informed consent must be obtained from every subject before entry into a clinical study. It must be given freely and not under duress. Consent must be documented by use of an IRB/ERC-approved consent form and signed by the subject or the subject's legally authorized representative. The US Department of Health and Human Services suggests that when minors are involved, a parent or guardian should sign the consent form. If the minor is an adolescent, his signature should also be included. Non-English-speaking subjects must be presented with

a consent form written in a language that they understand. A copy of the signed consent form must be given to the subject signing it. Another copy must be kept in the Investigator's files and made available to regulatory authority representatives upon request. If, for any reason, subject risk is increased as the study progresses, a revised, IRB/ERC-approved consent form must be signed by the subject. Before the study begins, a sample of the consent form must be provided to the Sponsor for review. The FDA and/or other applicable regulatory agencies may reject otherwise scientifically valid studies if proper informed consent has not been obtained from all subjects.

Only in the case of a life-threatening incident may an investigational product be used without prior signed consent. In such an emergency situation, separate certifications must be written both by a physician not participating in the study and by the Investigator. The certifications, along with the protocol and informed consent, must be sent to the IRB/ERC within 5 working days. In this situation, the Investigator may not administer any subsequent product to that subject until informed consent and IRB/ERC approval are obtained.

Informed Consent

Written informed consent must be obtained from each subject prior to entry in the study. One copy of the signed informed consent document will be given to the subject, and another will be retained by the Investigator. Additionally, the subject must be allowed adequate time to consider the potential risks and benefits associated with his/her participation in the study.

In situations where the subject is not legally competent to provide consent (ie, mentally incapacitated), written consent must be obtained from a parent, legal guardian, or legal representative. In these situations, the consent must be signed and dated by a witness.

The informed consent document must have been reviewed and approved by the Sponsor and by the Investigator's IRB/ERC prior to the initiation of the study. The document must contain the 8 basic elements of informed consent and may contain the 6 additional elements described in 21 CFR Part 50. Every consent form must include the following 8 elements:

- A statement that the study involves research, an explanation of the purpose of the research and the expected duration of the subject's participation, a description of the procedures to be followed, and identification of any procedures that are experimental
- A description of any reasonably foreseeable risks or discomforts to the subject
- A description of any benefits to the subject or to others that may reasonably be expected from the research
- A disclosure of appropriate alternative procedures or course of treatment, if any, that might be advantageous to the subject

- A statement describing the extent, if any, to which confidentiality of records identifying the subject will be maintained and noting the possibility that the FDA and/or other applicable regulatory authority representatives may inspect the records
- An explanation as to whether any compensation or medical treatments are available if injury occurs for research involving more than minimal risk. The explanation should involve a description of the compensation or treatment available, or a statement describing where further information may be obtained
- An explanation of whom to contact for answers to pertinent questions about the research and the subject's rights and whom to contact in the event of a research related injury
- A statement that participation is voluntary, that refusal to participate will involve no penalty or loss of benefits to which the subject is otherwise entitled, and that the subject may discontinue participation at any time without penalty or loss of benefits to which the subject is otherwise entitled.

When appropriate, 1 or more of the following elements of information shall also be included in the consent form:

- A statement that the particular treatment or procedure may involve risks to the subject (or to the embryo or fetus, if the subject is or may become pregnant) which are currently unforeseeable
- Anticipated circumstances under which the subject's participation may be terminated by the Investigator without regard to the subject's consent
